7.3. Unscheduled Visits

If, during the investigation, a subject requires an unscheduled visit to the clinical site, the following information will be collected at a minimum:

- Chief complaint prompting the visit. If the reason is an adverse event, the applicable eCRF for the adverse event must be completed and subject record completed as appropriate.
- Date and time of the visit and all procedures completed at the unscheduled visit.
- Review of adverse event and concomitant medications.
- Documentation of any test article dispensed or collected from the subject, if applicable.
- Slit lamp findings (using the Slit Lamp Classification Scale).

If the Investigator withdraws a subject from the study, the final study visit case report forms must be completed indicating the reason(s) why the subject was withdrawn. The subject record must be completed documenting the date and primary reason for withdrawal and the study CRA notified.

Any ocular and non-ocular Adverse Events that are ongoing at the time of the study visit will be followed by the Investigator, within licensure, until they have resolved, returned to pre-treatment status, stabilized, or been satisfactorily explained. If further treatment i.e., beyond licensure, is required, the subject will be referred to the appropriate health care provider.

The following information will be collected during an unscheduled visit.

Unscheduled Visit			
Step	Procedure	Details	[REDACTED]
U.1	Reason for unscheduled visit	Indicate if the only reason for the visit is that the subject requires additional test articles. If the reason is other than resupply of previously dispensed lenses, specify the reason for the visit.	
U.2	Chief Complaints (if applicable)	Record the subject's chief complaints for reasons for the unscheduled visit.	
U.3	Adverse Events and Concomitant Medications Review (if applicable)	Review any changes to the subject's medical history or concomitant medications from the previous study visit. Record any changes, and any adverse events.	

Clinical Study Protocol

Johnson & Johnson Vision Care, Inc.

Unscheduled Visit			
Step	Procedure	Details	
U.4	Entrance VA (if applicable)	Record the distance high contrast LogMAR visual acuity (OD, OS, and OU), and the type of visual correction being worn (study lenses, habitual lenses, distance spectacles or unaided).	
U.5	Subjective Sphero-cylindrical Refraction (if applicable)	Subjective sphero-cylindrical refraction will be performed on both eyes.	
U.6	Best corrected logMAR visual acuity (if applicable)	Distance high contrast visual acuity will be measured OD, OS and OU with the subjective refraction in place.	Appendix E: Eurolens Research SOP # 12A
U.7	Slit Lamp Biomicroscopy (if applicable)	FDA Slit Lamp Classification Scale will be used to grade the findings. If the clearance of the fluorescein needs to be expedited, preservative-free rewetting drops may be instilled.	Appendix F: Eurolens Research SOP # 13
U.8	Dispensing (if applicable)	If the subject requires additional lenses to complete the wear period and is eligible to do so, provide additional lenses per the dispensing instructions given in the detailed study procedures.	
U.9	Exit Visual Acuity (if applicable)	Record the distance high contrast LogMAR visual acuity (OD, OS, and OU), and the type of visual correction being worn (study lenses, habitual lenses, distance spectacles or unaided).	Appendix E: Eurolens Research SOP # 12A

Note: If the only reason for the unscheduled visit is that the subject requires additional test articles, only the dispensing information needs to be recorded.

7.4. Laboratory Procedures

Not applicable.

8. SUBJECTS COMPLETION/WITHDRAWAL

8.1. Completion Criteria

Subjects are considered to have completed the study if they:

- Provided informed consent.
- They are eligible.

Clinical Study Protocol

Johnson & Johnson Vision Care, Inc.

- Have completed all study visits.
- Have not withdrawn/discontinued from the study for any reason described in Section 8.2.

8.2. Withdrawal/Discontinuation from the Study

A subject will be withdrawn from the study for any of the following reasons:

- Subject withdrawal of consent.
- Subject not compliant to protocol including use of non-study lenses or not reaching the required wear times.
- Subject lost to follow-up.
- Subject no longer meets eligibility criteria (e.g. the subject becomes pregnant).
- Subject develops significant or serious adverse events causing discontinuation of study lens wear (more than 7 days).
- Subjects who have experienced a Corneal Infiltrative Event (CIE).
- Investigator's clinical judgment regarding the subject safety reasons (that it is in the best interest of the subject to stop treatment).
- Subject missed two consecutive study visits.
- Subject not compliant with study lens wear schedule.
- Subject not successfully dispensed due to lack of efficacy and safety including poor vision, poor comfort, or unacceptable fit.

For discontinued subjects, the Investigator will:

- Complete the current visit (scheduled or unscheduled).
- Complete the Final Evaluation, indicating the reason that the subject was discontinued from the study.
- Record the spherocylindrical refraction with best corrected distance visual acuity.
- Collect used test article(s) (worn or brought to the visit) from the subject and discard them, unless otherwise stated in Section 7.2.
- Collect all unused test article(s) from the subject.
- Make arrangements for subject care, if needed, due to their study participation.

Additional subjects will be enrolled if a subject discontinues from the study prematurely.

In cases where a subject is lost to follow-up, every possible effort must be made to contact the subject and determine the reason for discontinuation/withdrawal. The measures taken to follow up must be documented including two written attempts and a certified letter (or equivalent) as the final attempt.

9. PRE-STUDY AND CONCOMITANT INTERVENTION/MEDICATION

Concomitant medications will be documented during screening and updated during the study. Disallowed medications for this study include: any ocular topical medications (including comfort drops) and any systemic medications that in the view of the investigator may affect the ocular surface or contact lens wear from 24 hours prior to study visits.

Clinical Study Protocol

Johnson & Johnson Vision Care, Inc.

Concomitant therapies that are disallowed include: any that the investigator feels may significantly affect contact lens wear.

9.1. Systemic Medications

Certain systemic medications are known to have a higher likelihood to interfere with contact lens wear, chiefly by disrupting the tear film. A summary of disallowed medications is shown in Table 4. Subjects taking these medications on a continual, routine basis that have demonstrated successful contact lens wear for at least 6 months will generally be allowed to participate in this study. Subjects taking these medications on a routine basis but for less than 6 months will not be allowed to participate in the study.

NOTE: That subjects taking these medications on a temporary basis (e.g., antihistamines for seasonal allergy) will be allowed to participate if the medication has sufficient time to leave the body prior to the study. This is dependent on the half-life of the drug, body weight/fat, age, genetics, liver/kidney function, and metabolism of the subject. Given these unknowns, subjects taking the medications on a temporary basis must have ceased that medication at least 2 weeks prior to signing the informed consent.

Table 4: Disallowed systemic medications (less than 6 months of continual use).

Class of Drug	Common Indication(s)	Common Examples
Estrogens*	Menopause, osteoporosis, vaginitis	Vagifem, Estrace, Climara, Vivelle-Dot, Premarin, Minivelle, etc.
Antihistamines**	Allergic rhinitis, sedation, hives, allergic conjunctivitis, skin allergy, itching, motion sickness	Hydroxyzine, Promethagan, Phenadoz, Vistaril, Claritin, Zyrtec, Astepro, Astelin, Optivar, Pataday, Allegra, Benadryl, etc.
Anticholinergics	Irritable bowel syndrome, Parkinson's disease, peptic ulcer, cystitis, nasal congestion, cold symptoms, overactive bladder, COPD	Bentyl, Spiriva, Atrovent, Hyosyne, Levsin, Symax Fastab, Symax SL, Homax SL, Cogentin, Transderm Scop, etc.
Beta-blockers	Hypertension, angina, heart attack, migraine, atrial fibrillation, adrenal cancer, essential tumor, glaucoma	Toprol XL, Lopressor, Tenormin, Propranolol, Timoptic, Trandate, Inderal LA, etc.
Psychotropics	Antipsychotic (schizophrenia, mania), antidepression, antiobsessive, antianxiety, mood stabilizer, stimulants (ADHD)	Zoloft, Celexa, Prozac, Lexapro, Effexor, Cymbalta, Ativan, Xanax, Desyrel, Wellbutrin, etc.

Clinical Study Protocol

Johnson & Johnson Vision Care, Inc.

Class of Drug	Common Indication(s)	Common Examples
Vitamin A analogs	Cystic acne	Isotretinoin

*Contraceptive medication not included in this category

**Antihistamines allowed if taken continuously and demonstrated successful wear while taking the medication, or if they stopped taking the medication for at least 2 weeks prior to enrollment

10. DEVIATIONS FROM THE PROTOCOL

Investigator will notify study Sponsor upon identification of a protocol deviation. Protocol deviations must be reported to the Sponsor within 24 hours after discovery of the protocol deviation. The Investigator will report deviations per IRB/IEC requirements. All deviations will be tracked and corrective actions implemented as appropriate.

If it becomes necessary for the Investigator to implement a deviation in order to eliminate an immediate hazard to the trial subject, the Investigator may implement the deviation immediately without notification to the Sponsor. Within 24 hours after the implemented deviation, the Investigator must notify and provide the rationale to the Sponsor and, as required, to the IEC/IRB.

If the deviation potentially impacts the safety of patient or changes the technical integrity of the study then it must be reported to IEC/IRB. This is a "Major Deviation".

Minor deviations have no substantive effect on patient safety or technical integrity of the study. They are often logistical in nature. The informed consent must also not be contradicted by the deviation.

The prescribed visit window for Visit 2 is 7 to 14 days after Visit 1, and for Visit 3 it is 7 to 14 days after Visit 2. If subjects complete Visits 2 or 3 one to six days out of window this will be categorized as a minor protocol deviation. If subjects complete Visits 2 or 3 seven or more days out of window this will be categorized as a major protocol deviation. In the case of a major protocol deviation, the decision of whether or not the subject will be excluded from the Per-Protocol analysis population will be made at the time of cohort review.

Protocol waivers are prohibited.

11. STUDY TERMINATION

The occurrence of one or more Unanticipated Serious Adverse Device Effect (USADE), or any SAE where the relationship to study agent cannot be ruled out, may result in stopping further dispensing of test article. In the event of a USADE or SAE, the Sponsor may unmask the treatment regimen for the subject(s) and will discuss this with the Investigator before any further subjects are enrolled.

Clinical Study Protocol

Johnson & Johnson Vision Care, Inc.

The Sponsor will determine when a study will be stopped. The Principal Investigator always has the discretion to initiate stopping the study based on patient safety or if information indicates the study's results are compromised.

JJVC reserves the right to terminate the study at any time for any reason. Additionally, the IEC/IRB reserves the right to terminate the study if an unreasonable risk is determined. The study can be terminated by the Principal Investigator at the individual clinical site due to specific clinical observations, if in their opinion, after a discussion with JJVC, it is determined that it would be unwise to continue at the clinical site.

JJVC (and the IEC/IRB and DMC, if applicable) will evaluate all adverse events. If it is determined that an adverse event presents an unreasonable risk, the investigation, or that part of the investigation presenting the risk, will be terminated as soon as possible.

Should the study be terminated (either prematurely or as scheduled), the Investigator will notify the IEC/IRB and Regulatory Authority as required by local regulatory requirements.

12. PROCEDURE FOR HANDLING PRODUCT QUALITY COMPLAINTS

A Product Quality Complaint (PQC) refers to any written, electronic, or oral communication that alleges deficiencies related to the identity, quality, durability, reliability, safety, effectiveness or performance of test articles after they have been released for clinical trial use.

Potential complaints may come from a variety of sources including but not limited to subjects, clinical research associates (CRA), clinical operations managers (COM), medical monitors, and site personnel, etc. The following are not considered product quality complaints:

- Subject satisfaction inquiries reported via “Subjective Questionnaires” and “Patient Reported Outcomes (PRO)”.
- Clinical test articles that are stored improperly or damaged after receipt at the investigational site.
- Lens replacements that occur due to drops/fall-outs.
- Damage deemed by clinicians or clinical staff to be caused by handling by the user, and not indicative of a quality deficiency (i.e. tears, rips, etc.), only in situations where there is no deficiency alleged by the subject.

Within 24 hours of site personnel becoming aware that a PQC has occurred, the PQC must be recorded in the EDC system, which will trigger an automatic email notification to the appropriate COM/CRA and Clinical QA representative. In cases where the EDC system in use is not configured to send automatic notifications or when an EDC system is not used, the COM/CRA is responsible for notifying Clinical QA upon discovery that a PQC has occurred.

Upon receipt of the EDC notification, the COM/CRA will contact the study site to collect additional information which will include:

- Date the complaint was received/recorded in the EDC System (Date of Sponsor Awareness).

Clinical Study Protocol

Johnson & Johnson Vision Care, Inc.

- Who received the complaint.
- Study number.
- Clinical site information (contact name, site ID, telephone number).
- Lot number(s).
- Unique Subject Identifier(s).
- Indication of who first observed complaint (site personnel or subject).
- OD/OS indication, along with whether the lens was inserted.
- Any related AE number if applicable.
- Detailed complaint description (scheduled/unscheduled visit, wear time, symptoms, resolution of symptoms, etc.).
- Eye Care Provider objective (slit lamp) findings if applicable.
- Confirmation of product availability for return (and tracking information, if available), or rationale if product is not available for return [REDACTED]

Once a complaint is received, it will be assessed by the COM, CRA, or trained site personnel to determine if it is an Adverse Event/Serious Adverse Event (AE/SAE). If the complaint results in an AE/SAE, the COM/CRA, or trained site personnel will follow Section 13 of this protocol. If the AE/SAE was potentially the result of a product quality related deficiency, these procedures also apply and will be executed in parallel.

In some cases, a PQC form may be generated in EDC by the site in error. In this event, the PQC forms will be marked “Intentionally Left Blank” or “ILB”. Justification for ILB must be documented.

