5.2. Masking

This is a single masked study where subjects are masked to the identity of the study contact lenses during the study. The investigators and technical personnel involved in the data collection may be aware of the study lenses based on a slight difference in lens color (the Test lens will be slightly more turquoise in color than the Control lens).

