13.2. Assessing Adverse Events

In conjunction with the medical monitor, the Investigator will evaluate adverse events to ensure the events are categorized correctly. Elements of categorization will include:

- Seriousness/Classifications (see definition in Section 13.1).
- Causality or Relatedness – i.e. the relationship between the test article, study treatment or study procedures and the adverse event (not related; unlikely related; possibly related; related - see definition in Section 13.2.1).
- Adverse Event Severity – Adverse event severity is used to assess the degree of intensity of the adverse event (mild; moderate; severe for all events - see definition in Section 13.2.2).

Clinical Study Protocol

Johnson & Johnson Vision Care, Inc.

- Outcome – not recovered or not resolved; recovering or resolving; recovered or resolved with sequelae; recovered or resolved; death related to adverse event; unknown.
- Actions Taken – none; temporarily discontinued; permanently discontinued; other.

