Clinical Study Site: Location where a clinical study is conducted, such as a doctor's office, university, or laboratory. Clinical studies are conducted by Investigators who are individual(s) responsible for the conduct of the clinical study at a study site. If a study is conducted by a team of individuals, the Investigator is the responsible leader of the team and may be called the Principal Investigator.

Clinical Operations Manager (COM): The Johnson & Johnson Vision Care (JJVCI) individual responsible for the overall management of a clinical trial.

Monitor: An individual designated to oversee the progress of a clinical study and ensure that it is conducted, recorded, and reported in accordance with the protocol, Standard Operating Procedures (SOPs), Good Clinical Practice (GCP), and applicable regulatory requirements.

Medical Safety Officer (MSO): Physician who has primary accountability in their product portfolio for product health and safety, and who serves as an independent medical voice for patient safety.

Safety Management Team (SMT): A cross-functional, collaborative team responsible for review, assessment and evaluation of medical safety data arising from any source throughout the product life cycle.

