6.1 Monitoring Visits

When on-site monitoring by the sponsor is not feasible, the sponsor's site monitor will contact the study site to schedule remote visits. In such cases, on-site monitoring visits will resume when feasible, with increased frequency to address the source data verification backlog.

Even with staffing limitations during this COVID-19 pandemic, all routine operations related to clinical trials should be well-documented and archived as part of standard process. When conditions permit, all parties involved in this clinical trial should communicate relevant information in a timely manner so that all relevant parties remain sufficiently informed.

6.1.1 Study Site Initiation:

During the period that this Work Instruction is in effect, Site Initiation Meetings and training of study site staff will be conducted remotely. The JJVCI study team will conduct training via Skype, Zoom, Microsoft Teams or similar software as well as utilize online training materials, as applicable. Study site training will be documented utilizing Site Initiation Report [REDACTED] per Study Site Initiation [REDACTED]

On-site visits may be considered when, for example, hands-on training or evaluation of site facilities is required. While on site, the Clinical Research Associate (CRA) will follow all local, state, and governmental policies for COVID-19 Risk Mitigation, including social distancing, wearing of PPE, etc. as applicable for the location of the study site.

6.1.2 Interim Monitoring Visits (if applicable):

During the period that this Work Instruction is in effect, Interim Monitoring On-site visits will be kept to a minimum and include only those tasks that the CRA cannot perform remotely (e.g., source document verification, test article reconciliation, etc.).

To ensure data integrity during the conduct of all JJVC studies, clinical study teams will follow the study specific Clinical Monitoring Plan [REDACTED]

While on site, the CRA will follow all local, state, and governmental policies for COVID-19 Risk Mitigation, including social distancing, wearing of PPE, etc. as applicable for the location of the study site.

6.1.3 Study Site Closure:

During the period that this Work Instruction is in effect, the duration of the Study Site Closure Visit will be limited to tasks that the CRA cannot perform remotely (e.g., source document verification, test article final reconciliation and return, etc.).

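### Section 12 lets the COM, the CRA or trained site personnel alone decide whether a lens complaint is an AE/SAE, with no Investigator confirmation of a negative decision

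*Combined protocol and SAP*

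**What the plan says.** Section 12 says of a received complaint that "it will be assessed by the COM, CRA, or trained site personnel to determine if it is an Adverse Event/Serious Adverse Event (AE/SAE"). It continues: "If the complaint results in an AE/SAE, the COM/CRA, or trained site personnel will follow Section 13 of this protocol". The section states no step for a complaint judged not to be an event.

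Appendix H (Section 3.0) defines the COM as "The Johnson & Johnson Vision Care (JJVCI) individual responsible for the overall management of a clinical trial". Section 6.1 of that appendix describes CRA tasks such as source verification and lens reconciliation. Neither place states a clinical qualification. Trained site personnel are not defined further and may include clinicians.

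Section 13.2 reads: "In conjunction with the medical monitor, the Investigator will evaluate adverse events to ensure the events are categorized correctly". The first element it lists is "Seriousness/Classifications (see definition in Section 13.1"). Section 13.2.1 gives causality to the investigator, and Section 13.3 has the Principal Investigator document each event found.

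**The concern.** A complaint can carry clinical content. Section 12 counts alleged safety deficiencies as complaints and has the COM or CRA collect symptoms, their resolution and, where applicable, slit lamp findings. Whether such a report is an adverse event, and whether it is serious, is a clinical judgement. Several events listed in Section 13.1, such as peripheral ulcers and infiltrative events, are eye-care diagnoses.

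As written, that judgement may rest with one person who need not be a clinician, and a negative answer needs no countersignature. At stake are how quickly complaint-linked eye events are recognised and whether they are classified correctly. Section 13.4 requires serious and significant events to reach the sponsor within 24 hours of discovery, and Section 11 ties possible action on further dispensing to certain serious events. Both depend on the event being recognised as such.

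**Working it through.** The plan gives no figure on this point. The check sets the sections side by side, with one piece of arithmetic on timing.

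1. **Who decides on a complaint.** Section 12 joins the three roles with *or*, so one suffices. The Investigator and medical monitor are not named.

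2. **What follows.** A positive decision leads to Section 13. For a negative one, Section 12 asks for no confirmation and no recorded reason. It does require a documented justification when a complaint form was raised in error and is voided, but not when a genuine complaint is judged to be no event.

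3. **Overlap with Section 13.2.** Section 12 asks whether the complaint is an AE or an SAE, which includes seriousness. Section 13.2 gives seriousness to the Investigator with the medical monitor, so two sections assign that part to different people. On first recognition, 13.2 does not say who decides, so there the fault is an unaligned hand-off and not a direct contradiction.

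4. **Other routes to a clinician, and when they operate.**
   - Visits 2 and 3 (Section 7.2): adverse event review, open-ended symptom questions and graded slit lamp, whatever happened to the complaint. Table 3 puts each visit 7 to 14 days after the previous one.
   - Unscheduled visits (Section 7.3): adverse event review and slit lamp are in the minimum data set. If the only reason is more lenses, just the dispensing information is needed. A subject replacing a problem lens could fall here.
   - eCRFs (Section 15.1): reviewed and signed by the Investigator, with no timing set relative to the complaint decision.

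5. **Timing.** Assume a complaint arises just after fitting, is judged no event, and is next looked at clinically at the scheduled visit. The wait within the visit window is then:
   - shortest interval: 7 days × 24 = 168 hours
   - longest interval: 14 days × 24 = 336 hours

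   A complaint later in the period waits less. The Section 13.4 limit is 24 hours, counted from discovery. If discovery means receipt of the complaint, the limit is missed. If it means recognition of the event, the clock only starts at the visit. Either way the sponsor's medical review comes late.

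6. **Effect on the analysis.** The primary endpoint is lens fit acceptance, judged by the investigator at dispensing and follow-up (Sections 2.2 and 14.5). It does not pass through the complaint route. Only the completeness and classification of the descriptive safety summaries could be touched.

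**The case against.** The strongest reply is that Section 13 does not depend on Section 12. Section 13.3 requires every adverse event during enrolment to be documented, whatever its cause. Section 12 can be read as an added check for events hidden in product complaints. Complaints that site personnel learn of go into the EDC system within 24 hours. The COM or CRA then asks the site for any related event number and any slit lamp findings, so the form expects that an event may already be on record. Section 13.2 concerns categorising events already identified. The Medical Monitoring Plan is a separate document and is not available here.

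Most of this stands, and it rules out some stronger readings:

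- **A reader might infer that events are screened out before any clinician sees them.** The visit examinations, the unscheduled-visit rules and the eCRF signature show otherwise. A complaint handled only by the COM or CRA could miss early clinical review, but the plan as a whole gives later routes.
- **A reader might infer that non-clinical sponsor staff always decide.** Site personnel are a named option, and the documents do not state the qualifications of the COM or CRA either way.
- **A reader might infer a different event threshold for the sponsor's lens and the competitor's.** Section 5.2 says "This is a single masked study where subjects are masked to the identity of the study contact lenses during the study", so staff are not masked. But the same section says investigators may recognise the lens by its colour, and the synopsis calls the medical monitor the sponsor's. Moving the decision to them would not mask it, and nothing in the documents shows unequal handling.
- **A reader might express one missed event as a share of 10 or 16 subjects.** That only restates the sample size, and 16 is an enrolment cap counted from consent, not a number exposed.

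What the reply does not answer is the missing confirmation of a negative decision, the overlap on seriousness, and the delay before the backstops operate.

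**Conclusion.** The point holds as a misassigned safety decision with a limited consequence. Section 12 allows one person, not necessarily a clinician, to settle whether a complaint is an AE/SAE, requires no confirmation of a negative decision, and overlaps Section 13.2 on seriousness. The realistic harm is delay or misclassification of a complaint-linked eye event, not systematic loss of events. Within the visit windows the delay could reach 14 days, assuming the complaint comes just after fitting and no unscheduled examination intervenes. The documents give no basis for estimating how often this would happen. The primary endpoint and its analysis are unaffected. The change should be made because it is cheap and removes an inconsistency in safety handling.

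**What to change.** Amend Section 12 so that the COM, CRA and site staff record, triage and forward complaints. For every complaint that mentions an eye symptom, a slit lamp finding or lens removal, the Investigator, with the medical monitor as in Section 13.2, makes and signs the AE/SAE decision, including negative ones. Product-quality handling otherwise stays as it is.

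The cost is a short amendment to Section 12, a signature field on the complaint form, and a few minutes of Investigator time per complaint. The time is a judgement, since the documents give no expected number of complaints, but this is a single-site study with at most 16 enrolled.
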